AEs will be recorded starting with Screening. Once dosed, subjects will also be monitored for the occurrence and severity of indicators of reactogenicity. Treatment-emergent AEs (TEAEs) include all AEs that occur with and after dosing. It is expected that PHV01 may cause cytokine-mediated acute phase reactions similar to those associated with the similar Ebola vaccine (ERVEBO) during the first 1-3 days after inoculation (17). Thus, TEAEs will be solicited daily for 14 days after vaccination using a scripted questionnaire or Memory Aid (Section 5.4.1), including expected local and systemic AEs, as well as specific neurologic, joint, or dermatologic AEs, and unsolicited AEs; solicited AEs for Days 16-29 are limited to instances of neurological signs and symptoms, arthritis, and rash. Throughout the remainder of the study (e.g., until study day 181), subjects will be asked to report important changes in health status and concomitant medications, as well as any medically attended adverse events (MAAEs) (Section 5.4.2). AEs will be recorded throughout the rest of the study if noted on subsequent Memory Aids or if evaluated as MAAEs, serious AEs (SAEs), or AEs of special interest (AESIs), along with any concomitant medications (Section 6.4.3). The severity of all AEs will be graded in accordance with the FDA document "Guidance for Industry: Toxicity Grading Scale for Healthy Adult and Adolescent Volunteers Enrolled in Preventive Vaccine Clinical Trials" (APPENDIX 1).

Medically-Attended Adverse Events

Any AEs that cause a subject to seek medical care (including extra visits to the clinical site) are considered to be MAAEs. These will be recorded for the entire study. Subjects will be asked to record MAAEs on Memory Aids that will be reviewed during the visits on days 29, 85, and 181.

Adverse Events of Special Interest

In order to maximize the value of vaccine safety data in clinical trials, the CEPI and the Brighton Collaboration have formed an international organization, "Safety Platform for Emergency Vaccines" (SPEAC), to promote standardization of data collection, presentation, and analysis of AESIs relevant to vaccines in general, to specific vaccine platforms (live virus vaccines, rVSV vaccines), and in specific cases to the target disease itself (28).

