While Marburg disease cannot be acquired with PHV01 injection, as the only MARV component present is the GP gene in a background of rVSV, vaccines, in general, have been associated with neurologic disease (generalized convulsions, aseptic meningitis, optic neuritis, transverse myelitis, Guillain-Barré Syndrome (GBS), and acute disseminated encephalomyelitis (ADEM), hematologic disease (thrombocytopenia) and immunologic disease (anaphylaxis, vasculitides), and these conditions are considered AESIs in this study.

In order to capture vaccine-related AEs resembling those associated with WT MARV infection, AEs such as multiorgan failure, hemorrhagic diathesis, and neurologic complications (encephalitis, myelitis, aseptic meningitis, generalized convulsions) are considered AESIs.

Subjects' Memory Aids through day 181 will be reviewed for evidence of potential neurologic disease, i.e., blurry vision, changes in balance or coordination, confusion, disorientation, dizziness, severe headache, shaking or body tremors, slurred speech, tingling or numbness, weakness or

feeling weak. If present, a neurologic examination will be performed and documented. In addition, a neurologic examination will be performed and documented at baseline and day 29.

Neurologic examination will include assessment of affect, posture, involuntary movement, cognition, speech, cranial nerves, strength, gait, sensation, deep tendon reflexes, and coordination.

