3. STUDY DESIGN

3.1. STUDY ENDPOINTS

3.1.1. Primary Safety Endpoints

- Incidence and severity of solicited injection site AEs (arm pain, local tenderness, erythema (redness), induration (swelling/firmness) and systemic AEs (objective fever, subjective fever, chills, sweats, headache, myalgia, arthralgia, fatigue, nausea, vomiting) and neurological AEs (blurry vision, changes in balance or coordination, confusion, disorientation, dizziness, severe headache, shaking or body tremors, slurred speech, tingling or numbness, weakness or feeling weak) between days 1 and 8, and days 9-15 after vaccination, per treatment group (active vaccination versus placebo) and stratified by relatedness.
- Incidence and severity of unsolicited AEs between days 1-8, days 9-15, and up to day 29 after vaccination, per treatment group (active vaccination versus placebo) and stratified by relatedness.
- Incidence and severity of arthritis and skin/mucosal lesions up to day 29 after vaccination using standard case definitions and stratified by relatedness. This includes where possible quantitative reverse transcription polymerase chain reaction (RT-qPCR) for detection of PHV01 and lesion biopsy for histopathology.
- Incidence of SAEs observed up to day 181 and stratified by relatedness.
- Incidence and severity of MAAEs observed up to day 181 and stratified by relatedness.
- Physical and neurological examination results, vital signs, normal and abnormal clinical laboratory values (hematology and clinical chemistry, urinalysis).
- Incidence of adverse events of special interest (AESIs), to include pneumonitis, acute respiratory distress syndrome, multiorgan failure, a hemorrhagic diathesis, certain neurologic events (encephalitis, myelitis, aseptic meningitis, optic neuritis, transverse myelitis, generalized convulsions, Guillain-Barré Syndrome, acute disseminated encephalomyelitis), thrombocytopenia, anaphylaxis, and vasculitides.

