3.7.2. Stopping and Pausing Rules

Criteria for Study Pause or Halt

Study pause and halting criteria related to AEs are as follows:

The SRC will review the day 8 safety data in each Dosing Cohort to determine if enrollment may continue.

Dosing will be paused if 2 or more subjects experience the same or similar Grade 3 adverse event considered to be at least possibly related to vaccination. In the event of a study pause, the SRC will meet before resumption of dosing.

Dosing will be halted if a SAE or an AESI is considered anything other than not related to PHV01 vaccine. In the event dosing is halted, the SRC and IRB will review the event and other relevant safety data from the study and the IRB must agree before any continuation of dosing.

Enrollment

If no pause or halting rules are triggered in each Dosing Cohort, enrollment and dosing may proceed after review of day 8 safety data by the SRC. In the event dosing is paused or halted, scheduled follow up visits and procedures will continue for subjects already dosed.

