6.1. ASSESSMENT OF SAFETY

All AEs will be assessed as described in Section 6.4 according to the FDA document "Guidance for Industry: Toxicity Grading Scale for Healthy Adult and Adolescent Volunteers Enrolled in Preventive Vaccine Clinical Trials" (37), using toxicity grading tables excerpted from that guidance shown in APPENDIX 1: Clinical and Laboratory Toxicity Grading, Tables A1-A3. Safety will be assessed by evaluating reactogenicity (local reactions and systemic reactions) and the occurrence of post-vaccination solicited local reactions and systemic AEs through day 15. Solicited AEs for days 16-29 are limited to instances of neurological signs and symptoms, arthritis, and rash. Arthritis, rash, and neurologic events should be evaluated throughout the study and may include expert consultation.

Grading scales for laboratory value abnormalities are shown in APPENDIX 1: Clinical and Laboratory Toxicity Grading, Tables A4 and A5. Local laboratory normal ranges will be used to classify laboratory results. Clinically significant abnormal laboratory values will be graded as AEs according to the ranges specified in the table.

All vaccine-related SAEs must be reported as soon as possible following confirmation. The toxicity grading tables should be followed when determining the severity of an SAE.

Signs and symptoms of an AESI, as listed in Section 6.4.3, will be assessed throughout the study. If neurologic symptoms are present, a neurologic examination should be performed and documented. Neurologic examinations will also be performed at baseline and day 29.

The nature, frequency, and severity of MAAEs and SAEs from the time of injection through the final study visit should be recorded for each subject. MAAEs are defined as AEs leading to medically-attended visits that were not a routine visit for physical examination or vaccination, such as an emergency room visit or an otherwise unscheduled visit to or from medical personnel (medical doctor) for any reason.

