6.4.3. Adverse Events of Special Interest

The following are AESIs that will be monitored with increased frequency for safety purposes. AESIs that meet the serious criteria as defined in Section 6.4.4 will be reported as SAEs.

Respiratory Events:

• Acute respiratory distress syndrome/pneumonitis

Neurologic Events:

- ADEM
- Aseptic meningitis
- Encephalitis
- Generalized convulsions
- GBS
- Myelitis
 - o Optic neuritis
 - Transverse myelitis

Hematologic Events:

• Thrombocytopenia ≥ Grade 2

Immunologic Events:

- Anaphylaxis
- Vasculitides

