1.2.3. Stopping Rules and Unblinding

Criteria for Study Pause or Halt

The Safety Review Committee (SRC) will review the Day 8 safety data in each dosing cohort to determine if enrollment may continue. Dosing will be paused if 2 or more subjects experience the same or similar Grade 3 AE considered to be at least possibly related to vaccination. In the event of a study pause, the SRC will meet before resumption of dosing. Dosing will be halted if a serious adverse event (SAE) or an adverse event of special interest (AESI) is considered to be related to PHV01 vaccine. In the event dosing is halted, the SRC and Institutional Review Board (IRB) will review the event and other relevant safety data from the study and the IRB must agree before any continuation of dosing.

Enrollment

If no pause or halting rules are triggered in each dosing cohort, enrollment and dosing may proceed after review of Day 8 safety data by the SRC. In the event dosing is paused or halted, scheduled follow up visits and procedures will continue for subjects already dosed.

Individual Subject Unblinding

The group assignment for an individual subject may be unblinded during the course of the study if the Principal Investigator (PI) deems that, a safety event requires knowledge of that group assignment, the blind must be broken emergently to evaluate an AE; the other SRC members should be included in the decision if time allows. Only in the case of an emergency, when knowledge of whether the subject has received the investigational product (IP) is essential for

the clinical management or welfare of the subject, may the unblinded study pharmacist unblind that subject's treatment assignment. Unblinding at the study site for any other reason will be considered a protocol violation and reported as a major deviation.

Otherwise, the group assignments will be shared with the site, and subjects will be given the opportunity to request the identity of the IP he or she received, after the conclusion of all study visits (Day 1 to 181) and locking of the database.

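### Protocol 6.4.3, the AESI list that Section 6.1 sends sites to, omits multiorgan failure and hemorrhagic diathesis, and the AESI halting rule cites no list

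*Protocol*

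**What the plan says.** Five places describe the AESIs: Protocol 1.5.1, 3.1.1 and 6.4.3, and SAP 1.2.5.1 and 4.4.2.

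- Protocol 6.4.3 introduces its list with "The following are AESIs that will be monitored with increased frequency for safety purposes". The conditions follow under respiratory, neurologic, hematologic and immunologic headings, with nothing to mark them as examples.
- Protocol 6.1 points there: "Signs and symptoms of an AESI, as listed in Section 6.4.3, will be assessed throughout the study". Protocol 1.5.1 also cites Section 6.4.3 where it describes the recording of AESIs.
- Protocol 1.5.1, on events that resemble wild-type Marburg infection, states: "AEs such as multiorgan failure, hemorrhagic diathesis, and neurologic complications (encephalitis, myelitis, aseptic meningitis, generalized convulsions) are considered AESIs".
- Protocol 3.1.1 makes AESI incidence a primary safety endpoint: "Incidence of adverse events of special interest (AESIs), to include pneumonitis, acute respiratory distress syndrome, multiorgan failure, a hemorrhagic diathesis", followed by the remaining conditions. Both SAP lists name the same conditions.
- Protocol 3.7.2 ties halting to AESI status: "Dosing will be halted if a SAE or an AESI is considered anything other than not related to PHV01 vaccine". After a halt, the IRB must agree before dosing continues. SAP 1.2.3 restates the rule: dosing is "halted if a serious adverse event (SAE) or an adverse event of special interest (AESI) is considered to be related to PHV01 vaccine". Neither text says which AESI list applies.

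**The concern.** The section that directs day-to-day AESI assessment is the only one of the five that leaves out these two conditions. They are also the two non-neurologic AESIs that Protocol 1.5.1 adds in order to catch a vaccine effect resembling the target disease, so a deliberate narrowing is unlikely.

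What is at stake is mainly the halting rule. In a first-in-human dose escalation, one related AESI stops dosing, and whether an event is an AESI should not depend on which section the reader opens. Protocol 6.4.3 itself says that AESIs meeting the serious criteria are reported as SAEs, so a non-serious AESI is possible, and for such an event AESI status alone decides whether dosing halts. A lesser risk is that sites flag AESIs from 6.4.3 alone, so that the data feeding the endpoint are less complete than the SAP expects.

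**Working it through.** No calculation in the plan is in question. The check is a term-by-term comparison of the five descriptions.

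| Condition | Protocol 1.5.1 | Protocol 3.1.1 | Protocol 6.4.3 | SAP 1.2.5.1 | SAP 4.4.2 |
|---|---|---|---|---|---|
| Pneumonitis | no | yes | yes | yes | yes |
| Acute respiratory distress syndrome | no | yes | yes | yes | yes |
| Multiorgan failure | yes | yes | **no** | yes | yes |
| Hemorrhagic diathesis | yes | yes | **no** | yes | yes |
| Neurologic (encephalitis, myelitis, aseptic meningitis, optic neuritis, transverse myelitis, generalized convulsions, GBS, ADEM) | 8 | 8 | 8 | 8 | 8 |
| Thrombocytopenia | yes, no grade | yes, no grade | yes, Grade 2 or higher | yes, no grade | yes, Grade 2 or higher |
| Anaphylaxis | yes | yes | yes | yes | yes |
| Vasculitides | yes | yes | yes | yes | yes |
| Total | 13 | 15 | 13 | 15 | 15 |

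For 6.4.3 the sum is 2 respiratory + 8 neurologic + 1 hematologic + 2 immunologic = 13, and 15 − 13 = 2. Protocol 1.5.1 also reaches 13, but it is risk background and the two respiratory conditions that it lacks are in 6.4.3, so nothing turns on that.

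Next, follow a vaccine-related hemorrhagic diathesis through Protocol 3.7.2.

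1. It is judged serious. The SAE part of the rule halts dosing after 1 case, and the AESI list does not matter.
2. It is not judged serious, and the reader relies on Protocol 1.5.1 or 3.1.1. It is an AESI, so 1 case halts dosing and the IRB must agree before dosing resumes.
3. It is not judged serious, and the reader relies on 6.4.3 alone. It is not an AESI. The only automatic rule left is "Dosing will be paused if 2 or more subjects experience the same or similar Grade 3 adverse event" that is at least possibly related. That takes 2 subjects instead of 1, applies only at Grade 3, and leads to an SRC meeting without required IRB agreement.

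Cases 2 and 3 are the same event with different outcomes. Multiorgan failure would almost always fall under case 1, so in practice the omission matters for hemorrhagic diathesis.

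**The case against.** The strongest reply is that the Protocol, read as a whole, already makes both conditions AESIs. Section 1.5.1 says so without condition, Section 3.1.1 repeats it in a primary endpoint, and the halting rule does not confine itself to 6.4.3. The reference in 6.1 concerns assessment of signs and symptoms, the one in 1.5.1 concerns recording, and the opening of 6.4.3 could be read as naming a more closely watched subset. This stands as a limit. A reader might infer that the Protocol exempts a related hemorrhagic diathesis from halting, and the documents do not support that. They leave the governing list unstated, and 6.1 makes 6.4.3 a natural choice.

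The second reply is that other safeguards catch most such events:

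- Protocol 6.4.4 gives blood dyscrasias without hospitalization as an example of what may be judged serious.
- Protocol 6.5 makes every Grade 4 AE an SAE.
- Protocol 6.4.3 already lists thrombocytopenia of Grade 2 or higher.
- The SRC reviews day 8 data for each dosing cohort (3.7.2).
- Unanticipated problems go to the IRB within 24 hours (6.4.6).
- The investigator, the sponsor's representative, the SRC, the IRB or the FDA may stop use of the product at any time (3.7.3).

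This also stands, and it is why the point is minor. What these routes do not restore for a non-serious case is the automatic halt with required IRB agreement. Several of them rest on judgment, which a listing would make unnecessary.

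A reader might also try to define the uncovered events by the platelet, PT and PTT limits in Protocol Table A4. The documents do not support so sharp a boundary. The table's footnote calls its values guidelines, and there are other Grade 4 routes to an SAE, such as hemoglobin below 8.0 gm/dL in women or 8.5 gm/dL in men.

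**Conclusion.** The inconsistency is real and minor. Protocol 6.4.3 carries 13 of 15 AESIs and is the only one of five descriptions without multiorgan failure and hemorrhagic diathesis. The consequence is confined to a related hemorrhagic diathesis that is not judged serious, with a site or the SRC using 6.4.3 as the list. In that case the automatic response falls from a halt at 1 case, with IRB agreement needed to continue, to a pause at 2 similar Grade 3 cases.

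Two things are assumptions or judgments. That 6.4.3 would be used for halting is an assumption, because the rule cites no list. That the other safeguards catch most such events is a clinical judgment, for which the documents give no figure.

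A reader might infer that the primary AESI analysis is defective. The documents do not show that: the endpoint and both SAP lists name all 15 conditions, and the count would suffer only if sites flagged AESIs from 6.4.3 alone.

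**What to change.** Add multiorgan failure and hemorrhagic diathesis to Protocol 6.4.3. In the same amendment, have the halting rule in Protocol 3.7.2 cite Section 6.4.3 as its AESI list, and carry the citation into SAP 1.2.3. The two edits belong together: citing 6.4.3 before completing it would turn an ambiguity into a definite gap.

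Protocol 1.5.1 needs no additions for this purpose. Stating the Grade 2 threshold for thrombocytopenia wherever the condition is listed (Protocol 1.5.1 and 3.1.1, SAP 1.2.5.1) is optional tidying, since 6.4.3 and SAP 4.4.2 already agree on it.

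The cost is a short protocol amendment. Because it clarifies a halting trigger, it should go through the approvals in Protocol 10.3: the sponsor, the IRB or IEC and, where required, health authorities. The SAP change is one cross-reference. Visits, samples, sample size and analyses do not change.

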6.4.4. Serious Adverse Event or Serious Suspected Adverse Reaction

An AE or suspected adverse reaction is considered "serious" if, in the view of either the Investigator or Sponsor, it results in any of the following outcomes:

- Death
- Life-threatening AE, defined as any adverse drug experience that, in the opinion of the Investigator, places the subject at immediate risk of death from the reaction as it occurred. It does not include a reaction that, had it occurred in a more severe form, might have caused death.
- Inpatient hospitalization or prolongation of existing hospitalization
- Persistent or significant disability/incapacity defined as a "substantial disruption of the ability to conduct normal life functions"
- Congenital anomaly/birth defect (in the offspring of a subject)

Important medical events that may not result in death, be life-threatening, or require hospitalization may be considered serious when, based upon appropriate medical judgment, they may jeopardize the participant and may require medical or surgical intervention to prevent one of the outcomes listed in this definition. Examples of such medical events include allergic bronchospasm requiring intensive treatment in an emergency room or at home; blood dyscrasias or convulsions that do not result in inpatient hospitalization; or the development of drug dependency or drug abuse.

6.4.5. Unexpected Adverse Events or Unexpected Suspected Adverse Reactions

An AE or suspected adverse reaction is considered "unexpected" if it is not listed in the Investigator's Brochure (IB) or is not listed at the specificity or severity that has been observed. For example, under this definition, hepatic necrosis would be unexpected (by virtue of greater severity) if the IB referred only to elevated hepatic enzymes or hepatitis. Similarly, cerebral thromboembolism and cerebral vasculitis would be unexpected (by virtue of greater specificity) if the IB listed only cerebral vascular accidents. "Unexpected," as used in this definition, also refers to AEs or suspected adverse reactions that are mentioned in the IB as occurring with a class of biologics or as anticipated from the pharmacological properties of the biologic but are not specifically mentioned as occurring with the particular biologic under investigation.

6.4.6. Unanticipated Problems Involving Risks to Subjects or Others

Unanticipated problems involving risks to subjects or others must be reported to the IRB within 24 hours. These events encompass a broader category of events than SAEs and may include issues

such as problems with loss of control of subject data or the IP; adverse psychological reactions; or breach of confidentiality. Risks to others (e.g., program personnel) must also be reported.

Unanticipated problems involving risks to subjects or others are any incident, experience, or outcome that meets all of the following criteria:

- Unexpected (in terms of nature, severity, or frequency) given (a) the procedures that are described in the protocol, IB or ICF, and (b) the characteristics of the subject population.
- Related or possibly related to a subject's participation in the study.
- Suggests that the study places subjects or others at a greater risk of harm than was previously known or recognized.

The IRB will evaluate the PI's and Medical Monitor's reports to determine whether a given incident, experience, or outcome constitutes an unanticipated problem involving risk to subjects or others and, in coordination with the Sponsor, will ensure upward reporting of the unanticipated problems involving risk to subjects or others to the appropriate regulatory offices.

6.5. SEVERITY ASSESSMENT

All AEs will be assessed for severity by the Investigator. Inherent in this assessment is the medical and clinical consideration of all information surrounding the event, including any medical intervention required. Each event will be assigned one of the following categories: mild, moderate, severe, or life-threatening. Refer to the grading scale in APPENDIX 1 for further guidance in the assignment of severity. Any Grade 4 (life-threatening) AE must be reported as an SAE.

The eCRF for AEs will reflect only the highest severity for continuous days an event occurred. The following criteria below may be used for any symptom not included in the grading scale:

Mild (Grade 1): Does not interfere with routine activities; minimal level of discomfort.

Moderate (Grade 2): Interferes with routine activities; moderate level of discomfort.

Severe (Grade 3): Unable to perform routine activities; significant level of discomfort.

Potentially life-threatening (Grade 4): Hospitalization or ER visit for potentially life-threatening event.

The FDA guidelines for toxicity will be followed; however, if a subject is evaluated in an emergency room for nonlife threatening illness or symptoms (i.e., visits emergency department on weekend for mild problems because the physician's office is closed), the information from that visit will be reviewed and severity of the AE will be assessed according to the subject's clinical signs and symptoms.

As defined by the ICH guideline for GCP, the term "severe" is often used to describe intensity (severity) of a specific event (as in mild, moderate, or severe myocardial infarction); the event itself, however, may be of relatively minor medical significance (such as severe headache). This is **not** the same as "serious", which is based on subject/event **outcome** or **action** criteria usually associated with events that pose a threat to a subject's life or functioning. Seriousness (not severity) serves as a guide for defining regulatory reporting obligations.

